#### Assessment of Causality

- The investigator is obligated to assess the relationship between study intervention and each occurrence of each AE/SAE.
- A "reasonable possibility" of a relationship conveys that there are facts, evidence, and/or arguments to suggest a causal relationship, rather than a relationship cannot be ruled out.
- The investigator will use clinical judgment to determine the relationship.
- Alternative causes, such as underlying disease(s), concomitant therapy, and other risk factors, as well as the temporal relationship of the event to study intervention administration will be considered and investigated.
- The investigator will also consult the Investigator's Brochure (IB) and/or Product Information, for marketed products, in his/her assessment.
- For each AE/SAE, the investigator must document in the medical notes that he/she has reviewed the AE/SAE and has provided an assessment of causality.
- There may be situations in which an SAE has occurred and the investigator has minimal information to include in the initial report to the sponsor. However, it is very important that the investigator always make an assessment of causality for every event before the initial transmission of the SAE data to the sponsor.
- The investigator may change his/her opinion of causality in light of follow-up information and send a SAE follow-up report with the updated causality assessment.
- The causality assessment is one of the criteria used when determining regulatory reporting requirements.

• If the investigator does not know whether or not the investigational product caused the event, then the event will be handled as "related to investigational product" for reporting purposes, as defined by the sponsor" and "In addition, if the investigator determines that an SAE is associated with study procedures, the investigator must record this causal relationship in the source documents and CRF, and report such an assessment in the dedicated section of the CT SAE Report Form and in accordance with the SAE reporting requirements.

# Follow-up of AEs and SAEs

- The investigator is obligated to perform or arrange for the conduct of supplemental measurements and/or evaluations as medically indicated or as requested by the sponsor to elucidate the nature and/or causality of the AE or SAE as fully as possible. This may include additional laboratory tests or investigations, histopathological examinations, or consultation with other health care professionals.
- New or updated information will be recorded in the originally completed CRF.
- The investigator will submit any updated SAE data to the sponsor within 24 hours of receipt of the information.

### 10.3.4. Reporting of SAEs

### SAE Reporting to Pfizer Safety via an Electronic Data Collection Tool

- The primary mechanism for reporting an SAE to Pfizer Safety will be the electronic data collection tool.
- If the electronic system is unavailable, then the site will use the paper SAE data collection tool (see next section) in order to report the event within 24 hours.
- The site will enter the SAE data into the electronic system as soon as it becomes available.
- After the study is completed at a given site, the electronic data collection tool will be taken off-line to prevent the entry of new data or changes to existing data.
- If a site receives a report of a new SAE from a study participant or receives updated data on a previously reported SAE after the electronic data collection tool has been taken off-line, then the site can report this information on a paper SAE form (see next section) or to Pfizer Safety by telephone.

• Contacts for SAE reporting can be found in the investigator site file.

# SAE Reporting to Pfizer Safety via Paper CRF

- Facsimile transmission of the SAE paper CRF is the preferred method to transmit this information to Pfizer Safety.
- In rare circumstances and in the absence of facsimile equipment, notification by telephone is acceptable with a copy of the SAE data collection tool sent by overnight mail or courier service.
- Initial notification via telephone does not replace the need for the investigator to complete and sign the SAE CRF pages within the designated reporting time frames.
- Contacts for SAE reporting can be found in the investigator site file.

# 10.4. Appendix 4: Contraceptive Guidance and Collection of Pregnancy Information

**Definitions:** 

Woman of Childbearing Potential (WOCBP)

A woman is considered fertile following menarche and until becoming post-menopausal unless permanently sterile (see below).

If fertility is unclear (eg, amenorrhea in adolescents or athletes) and a menstrual cycle cannot be confirmed before first dose of study intervention, additional evaluation should be considered.

Women in the following categories are not considered WOCBP

- 1. Premenarchal
- 2. Premenopausal female with 1 of the following:
  - Documented hysterectomy
  - Documented bilateral salpingectomy
  - Documented bilateral oophorectomy

For individuals with permanent infertility due to an alternate medical cause other than the above, (eg, mullerian agenesis, androgen insensitivity), investigator discretion should be applied to determining study entry.

Note: Documentation for any of the above conditions can come from the site personnel's review of the participant's medical records, medical examination, or medical history interview. The method of documentation should be recorded in the participant's medical record for the study.

- 3. Postmenopausal female
  - A postmenopausal state is defined as age 60 or older or no menses for 12 months without an alternative medical cause.
    - A high follicle stimulating hormone (FSH) level in the postmenopausal range may be used to confirm a postmenopausal state in women not using hormonal contraception or hormonal replacement therapy (HRT).
  - Females on HRT and whose menopausal status is in doubt will be required to use one of the non-estrogen hormonal highly effective contraception methods if they wish to continue their HRT during the study. Otherwise, they must discontinue HRT to allow confirmation of postmenopausal status before study enrollment.

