- The use of a strong CYP3A4/5 inducer (eg, carbamazepine, enzalutamide, mitotane, phenytoin, rifampin, St. John's Wort) with lorlatinib is contraindicated and it should be avoided, if possible, as they may also reduce lorlatinib plasma concentration Furthermore, when lorlatinib was coadministered with rifampin (Study B7461011), increases in AST and ALT were noted. Discontinue strong CYP3A inducers for 3 plasma half-lives of the strong CYP3A inducer prior to initiating lorlatinib and until study treatment discontinuation. In addition, use with moderate CYP3A inducers should be avoided due to the potential reduction in lorlatinib exposure.
- Lorlatinib inhibits CYP2C9 (in vitro), so concurrent use of drugs that are CYP2C9 substrates with narrow therapeutic indices, such as warfarin, phenytoin or celecoxib, may have increased effect. Concomitant CYP2C9 substrates should be used with caution, as the net clinical effect of lorlatinib on CYP2C9 is currently being investigated.
- Lorlatinib induces CYP2B6 (in vitro) so concurrent use of drugs that are CYP2B6 substrates, such as bupropion and efavirenz, may have less effect. Concomitant CYP2B6 substrates (e.g. bupropion, efavirenz) should be used with caution, as the net clinical effect of lorlatinib on CYP2B6 is currently being investigated.
- In vitro studies indicated that lorlatinib is a time-dependent inhibitor as well as an inducer of CYP3A4/5 and it activates the human pregnane-X-receptor (PXR), with the net effect in vivo being induction. Thus, concurrent administration of lorlatinib with CYP3A4/5 substrates with narrow therapeutic indices, including but not limited to alfentanil, ciclosporin dihydroergotamine, ergotamine, fentanyl, hormonal contraceptives, pimozide, quinidine, sirolimus and tacrolimus, should be avoided since the concentration of these medicinal products may be reduced by lorlatinib. However, if it is absolutely necessary to use, sponsor approval is required and the dose of the CYP3A4/5 substrate may need to be increased. The narrow therapeutic index (NTI) CYP3A4/5 substrate should be started only after at least 14 days of

continuous lorlatinib dosing. If there is a change in the lorlatinib dosing regimen such as a dosing interruption or dose reduction, the administration of the NTI CYP3A4/5 substrate should be stopped and resumed at a readjusted dose only after at least 14 days of resumed lorlatinib dosing.

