### Contraception Guidance:

### Contraception - for women

Female participants must use highly effective contraception while taking study intervention and for at least 35 days after stopping study intervention.

Lorlatinib may reduce the effectiveness of hormonal contraceptive methods; therefore, hormonal contraceptives may not be considered highly effective. If hormonal contraception is unavoidable it must be used in combination with a condom.

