# Highly Effective Methods That Have Low User Dependency

- Intrauterine device (IUD).
- Bilateral tubal occlusion.
- Vasectomized partner.
  - Vasectomized partner is a highly effective contraceptive method provided that
    the partner is the sole sexual partner of the WOCBP and the absence of sperm
    has been confirmed. If not, an additional highly effective method of
    contraception should be used. The spermatogenesis cycle is approximately 90
    days.

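### Contraception wording in Appendix 4 and Section 6.5.1 is inconsistent for two small groups of women: HRT continuers and users of the hormonal-plus-condom route

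*Protocol*

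**What the plan says.** Three parts of the protocol bear on this.

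- **Appendix 4, definition of a postmenopausal female.** "Females on HRT and whose menopausal status is in doubt will be required to use one of the non-estrogen hormonal highly effective contraception methods". The sentence then limits this to women who want to stay on HRT. The others must come off it before enrolment so that menopausal status can be confirmed.
- **Appendix 4, contraception for women.** The standard is: "Female participants must use highly effective contraception while taking study intervention and for at least 35 days after stopping study intervention". Because lorlatinib may weaken hormonal methods, "hormonal contraceptives may not be considered highly effective". A fallback follows: "If hormonal contraception is unavoidable it must be used in combination with a condom". The list headed "Highly Effective Methods That Have Low User Dependency" has three entries: an IUD, bilateral tubal occlusion and a vasectomized partner. None is labelled hormonal.
- **Section 6.5.1.** The narrow-therapeutic-index CYP3A4/5 substrates, "including but not limited to alfentanil, ciclosporin dihydroergotamine, ergotamine, fentanyl, hormonal contraceptives" among them, "should be avoided since the concentration of these medicinal products may be reduced by lorlatinib". The exception is that "if it is absolutely necessary to use, sponsor approval is required". Two timing rules apply to the whole class. A substrate is not to be begun until lorlatinib has been taken continuously for 14 days or more. If lorlatinib is interrupted or reduced, the substrate is to be stopped, and restarted only once dosing has been back in place for 14 days or more.

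Inclusion criterion 12b asks women of childbearing potential for a method with an annual failure rate below 1%, during the intervention period and for 35 days afterwards. Section 8.2.6 has contraception in place after the negative screening test, before the first dose.

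**The concern.** The HRT sentence points to a hormonal method as highly effective, while the guidance that follows it in the same appendix says hormonal methods may not count as such on this drug. A site that follows the sentence literally would accept a method the protocol elsewhere regards as doubtful.

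The 14-day rule fits contraceptives poorly. For a drug whose level shifts with lorlatinib, stopping and re-titrating around a dose change is a sensible precaution. For a contraceptive, the worry stated in Appendix 4 is lost effectiveness, and stopping the method makes that worse. (The protocol gives no reason for the stop rule, so this account of its purpose is my inference.) Dose changes are also routine: Section 6.6, Table 3 calls for a hold and then a one-level reduction for Grade 2 or 3 CNS effects and for other reactions of Grade 3 or higher.

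What is at stake is the protocol's own protection against embryo-fetal exposure. No estimate, sample size or analysis is involved.

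**Working it through.** The protocol gives no figure of its own to reproduce. The check is a comparison of texts plus the length of the condom-only windows.

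**HRT sentence**
1. A woman who stays on HRT with doubtful menopausal status is directed to a method that is non-estrogen, hormonal and highly effective.
2. Appendix 4 then says hormonal methods may not be regarded as highly effective with lorlatinib.
3. No entry in the list of highly effective methods is labelled hormonal.
4. On the natural reading, the class named in step 1 therefore has no member in the list.

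**14-day rule, for a woman on the sponsor-approved hormonal-plus-condom route**

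Inputs: 14-day minimum (Section 6.5.1); toxicity hold of at most 42 days since last dose (Section 7.1.1); two reductions, 100 to 75 to 50 mg (Section 6.6); cover for 35 days after the last dose (criterion 12b and Appendix 4); 21-day cycles with checks every cycle ±2 days (Section 1.3.2).

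Condom-only time if the rule is followed = hold length L + at least 14 days.

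- Reduction without a hold, L = 0: at least 14 days, all on drug.
- Shortest hold, L = 1: 1 + 14 = at least 15 days.
- Longest toxicity hold, L = 42: 42 + 14 = about 56 days, of which 42 are off drug and 14 on drug.
- Both reductions: 2 × 14 = at least 28 on-drug days in total.
- Hormonal method newly started: at least the first 14 of the 21 days of Cycle 1 (14/21 = 67%).

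Apart from the 42-day limit on L, these are minima, because the rule sets a floor of 14 days.

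Off-drug days still need cover. The 35-day requirement alone reaches day 35 of a hold. The remaining 42 − 35 = 7 days count if a temporary hold is read as part of the intervention period, which is my reading.

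**Would the scheduled checks catch the gap?** Consecutive checks are 21 days apart, or 21 − 2 − 2 = 17 days at the shortest. Since 14 < 17, a 14-day gap can lie between two scheduled checks. Section 7.1.1 adds contacts, however. A reduction within a cycle brings the woman to the clinic for new supply, and a hold running past Day 21 makes the restart Day 1 of a new cycle, when checks fall due. These contacts let the site act, but no text tells it what to do about contraception.

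**Established users.** The start rule applies clearly only to a woman newly starting a hormonal method. Exclusion 13c bars narrow-therapeutic-index CYP3A substrates in the 12 days before the first dose, but its examples do not name hormonal contraceptives, so the position of an existing user is unclear.

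**The case against.** A reader might infer that these instructions cannot all be followed, or that a site must breach one section to obey another. The documents do not support that.

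- A woman using a listed non-hormonal method satisfies every section, and criterion 12b prefers methods with low user dependency.
- The HRT sentence is conditional, and stopping HRT is an open alternative.
- Section 6.5.1 opens by leaving necessary treatment to the treating physician and presents its items as cautions. Its contraceptive rules are worded as advice, whereas Appendix 4 uses mandatory language. A physician who keeps the hormonal method going through a dose change is using that discretion to meet the stronger instruction.
- The hormonal-plus-condom route needs sponsor approval under Section 6.5.1. It is also already an exception to the highly effective standard, so the 14-day rule does not by itself create that shortfall.
- The wording allows milder readings. The HRT phrase could mean any method that is not estrogen-based, which an IUD would meet, and the Appendix 4 warning could mean only that hormonal methods might not qualify.

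All of this stands and limits the point. What survives is narrower. The literal 14-day rule removes the hormonal half of a combination that Appendix 4 says must be used together. The HRT sentence, on its natural reading, names a class that the rest of the appendix does not recognise. The discretion in Section 6.5.1 permits a sensible outcome but does not say what it should be.

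**Conclusion.** The contraception wording is internally inconsistent for two small groups: women with doubtful menopausal status who continue HRT, and women relying on the hormonal-plus-condom fallback who start the hormonal method on study or have a dose change. For the second group, following Section 6.5.1 to the letter means a condom alone for at least 14 on-drug days after each reduction. After an interruption it means the hold plus at least 14 days, up to about 56 days for a toxicity hold at the limit.

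This rests on the natural reading of the HRT phrase and on the 14-day rule applying to hormonal contraceptives because Section 6.5.1 names them in the class. The number of women concerned is not given; it would be a subset of the planned 70 participants. The point concerns participant protection and has no bearing on the primary endpoint or any analysis. It is worth correcting because the literal text gives less protection than the protocol intends.

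**What to change.** Two wording changes.

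- **Appendix 4, HRT sentence.** Ask for a non-hormonal highly effective method, as listed in Appendix 4, in place of the non-estrogen hormonal one. Stopping HRT remains the alternative.
- **Section 6.5.1.** Keep the advice to avoid hormonal contraceptives and the need for sponsor approval. Then add one of two statements: that the 14-day start and stop rule does not apply to hormonal contraceptives, with a cross-reference to Appendix 4; or that a non-hormonal method listed in Appendix 4 must be in place before a hormonal method is stopped.

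A flat ban on stopping a hormonal method is not needed; the exemption or the bridging requirement closes the gap. Whether to keep the hormonal-plus-condom fallback is a clinical decision for the sponsor, and neither change depends on it.

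The cost is one phrase and one bullet, with matching consent text if it repeats them. There is no cost in data, sample size or analysis.

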### Contraception Guidance:

### Contraception - for women

Female participants must use highly effective contraception while taking study intervention and for at least 35 days after stopping study intervention.

Lorlatinib may reduce the effectiveness of hormonal contraceptive methods; therefore, hormonal contraceptives may not be considered highly effective. If hormonal contraception is unavoidable it must be used in combination with a condom.

# Highly Effective Methods That Have Low User Dependency

- Intrauterine device (IUD).
- Bilateral tubal occlusion.
- Vasectomized partner.
  - Vasectomized partner is a highly effective contraceptive method provided that
    the partner is the sole sexual partner of the WOCBP and the absence of sperm
    has been confirmed. If not, an additional highly effective method of
    contraception should be used. The spermatogenesis cycle is approximately 90
    days.

# Contraception - for men

Male participants must use a condom while taking study intervention and for at least 98 days after stopping study intervention.

Collection of Pregnancy Information:

For both unapproved/unlicensed products and for marketed products, an EDP occurs if:

- A female becomes, or is found to be, pregnant either while receiving or having been exposed (eg, because of treatment or environmental exposure) to the study intervention; or the female becomes or is found to be pregnant after discontinuing and/or being exposed to the study intervention;
  - An example of environmental exposure would be a case involving direct contact with a Pfizer product in a pregnant woman (eg, a nurse reports that she is pregnant and has been exposed to chemotherapeutic products).
- A male has been exposed (eg, because of treatment or environmental exposure) to the study intervention prior to or around the time of conception and/or is exposed during his partner's pregnancy.

If a participant or participant's partner becomes or is found to be pregnant during the participant's treatment with the study intervention, the investigator must report this information to Pfizer Safety on the CT SAE Report Form and an EDP supplemental form, regardless of whether an SAE has occurred. In addition, the investigator must submit information regarding environmental exposure to a Pfizer product in a pregnant woman (eg, a participant reports that she is pregnant and has been exposed to a cytotoxic product by inhalation or spillage) to Pfizer Safety using the EDP supplemental form. This must be done irrespective of whether an AE has occurred and within 24 hours of awareness of the exposure. The information submitted should include the anticipated date of delivery (see below for information related to termination of pregnancy).

Follow-up is conducted to obtain general information on the pregnancy and its outcome for all EDP reports with an unknown outcome. The investigator will follow the pregnancy until completion (or until pregnancy termination) and notify Pfizer Safety of the outcome as a follow-up to the initial EDP supplemental form. In the case of a live birth, the structural integrity of the neonate can be assessed at the time of birth. In the event of a termination, the reason(s) for termination should be specified and, if clinically possible, the structural integrity of the terminated fetus should be assessed by gross visual inspection (unless preprocedure test findings are conclusive for a congenital anomaly and the findings are reported).

If the outcome of the pregnancy meets the criteria for an SAE (ie, ectopic pregnancy, spontaneous abortion, intrauterine fetal demise, neonatal death, or congenital anomaly [in a live-born baby, a terminated fetus, an intrauterine fetal demise, or a neonatal death]), the investigator should follow the procedures for reporting SAEs.

Additional information about pregnancy outcomes that are reported to Pfizer Safety as SAEs follows:

- Spontaneous abortion includes miscarriage and missed abortion;
- Neonatal deaths that occur within 1 month of birth should be reported, without regard to causality, as SAEs. In addition, infant deaths after 1 month should be reported as SAEs when the investigator assesses the infant death as related or possibly related to exposure to the study intervention.

Additional information regarding the EDP may be requested by the sponsor. Further follow-up of birth outcomes will be handled on a case-by-case basis (eg, follow-up on preterm infants to identify developmental delays). In the case of paternal exposure, the investigator will provide the participant with the Pregnant Partner Release of Information Form to deliver to his partner. The investigator must document in the source documents that the participant was given the Pregnant Partner Release of Information Form to provide to his partner.

# 10.5. Appendix 5: RECIST (version 1.1) Tumor Assessment Criteria

At baseline, individual tumor lesions will be categorized by the investigator as either measurable or not, according to the criteria summarized below:

# Measurable Lesions

Lesions that can be accurately measured in at least one dimension (longest diameter in the plane of measurement is to be recorded) with a minimum size of:

- 10 mm for lesions other than lymph nodes and assessed by CT scan (CT scan slice thickness no greater than 5 mm)
- 10 mm for lesions assessed clinically by caliper measurement (lesions which cannot be accurately measured with calipers should be recorded as non-measurable).
- 20 mm for lesions assessed by chest X-ray.
- 15 mm in short axis for lymph nodes when assessed by CT scan (CT scan slice thickness recommended to be no greater than 5 mm).

